9. NON-STANDARD DATA DERIVATION RULES AND STATISTICAL METHODS

The following sections describe additional derivation rules and statistical methods which are not presented in section 10.1.

9.1. Handling of missing data

9.1.1. Dates

When partially completed dates (i.e. with missing day or month) are used in calculations, the following rules will be applied:

- Adverse event start dates with missing day:
 - If the month is not the same as the vaccine dose, then the imputed start date will be the 1st of the month
 - If the event starts in the same month as the vaccine dose, the flag indicating if the event occurred before or after vaccination (AE.AESTRTPT) will be used to complete the date. If ‘after vaccination’ is selected, the imputed start date will match the vaccine dose given during that month. If ‘before

CONFIDENTIAL

208851 (RSV OA=ADJ-002)
 Statistical Analysis Plan Amendment 2

vaccination' is selected, the imputed date will be one day before the vaccine dose given during that month.

- Adverse event start dates with missing day and month:
 - If the year is not the same as the vaccine dose, then the imputed start date will be the 1st of January.
 - If the event starts in the same year as the vaccine dose, the flag indicating if the event occurred before or after vaccination (AE.AESTRTPT) will be used to complete the date. If 'after vaccination' is selected, the imputed start date will match the first vaccine dose given during that year. If 'before vaccination' is selected, the imputed date will be one day before the first vaccine dose given during that year.
- Adverse event end dates with missing day: the imputed end date will be the last day of the month (30 or 31) or the study conclusion date whichever comes first.
- Adverse event end dates with missing day and month: the imputed end date will be the last day of the year (31st of December) or the study conclusion date whichever comes first.

All other cases of incomplete AE or concomitant medication/vaccination start date will follow the standard rules above.

9.2. Duration of events

When a solicited AE is ongoing at the end of the solicited follow up period (Day 7), the following rules will be applied:

- If the event is present at Day 7 and information is available at each day up to the end of the event: count number of days with event up to last day reported
- If information is missing at several days between the first day with the event and the end of event: count missing days as days with an event (worst case scenario)
- For Grade 3 AEs: take into account the grading of the last day with AE reported (last observation carried forward)

CONFIDENTIAL208851 (RSV OA=ADJ-002)
Statistical Analysis Plan Amendment 2

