5.4.2. Additional considerations

All analyses will be descriptive and will be based on the Exposed Set (ES).

Compliance in completing solicited adverse events information will be tabulated after each dose and overall.

The percentage of subjects with at least **one local solicited** AE, with at least **one general solicited** AE and with **any solicited** AE during the 7-day follow-up period will be tabulated with exact 95% confidence interval (CI) after each dose and overall. The same computations will be done for Grade 3 AEs, for any AEs considered related to vaccination, and for Grade 3 AEs considered related to vaccination.

The number of days with solicited symptoms reported during the **7-day follow-up period** will be tabulated for each solicited adverse event, after each dose using descriptive statistics (mean, min, Q1, median, Q3, maximum).

The same tabulation will be done for Grade 3 symptoms, and also during **the whole post-vaccination period** (to include the total number of days for symptoms ongoing beyond the follow-up period).

The incidence of each solicited symptom (any grade and grade 3) will also be represented graphically per group and per dose.

Analysis of solicited symptoms will also be done:

- on the **pooled groups according to adjuvant content** (AS01B, AS01E, Plain), overall and by age category.
- On symptoms reported during the 4-day period, i.e. on the day of vaccination and 3 subsequent days, for each group after each dose and overall.

CONFIDENTIAL

208851 (RSV OA=ADJ-002)
 Statistical Analysis Plan Amendment 2

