5.4.2.1. Solicited Adverse Events

Solicited adverse events will be reported daily during the 7-day (from Day 1 to Day 7) follow up period after each vaccination, using structured diaries. Missing or non-evaluable measurements will not be replaced.

In order to summarize the data, the maximum intensity of local injection site redness/swelling (in mm) and fever (in °C) will be categorized as follows:

Grading	Redness/swelling	Fever
0:	≤ 20 mm	< 38.0°C (100.4°F)
1:	> 20 - ≤ 50 mm	≥ 38.0°C (100.4°F) - ≤ 38.5°C (101.3°F)
2:	> 50 - ≤ 100 mm	> 38.5°C (101.3°F) - ≤ 39.0°C (102.2°F)
3:	> 100 mm	> 39.0°C (102.2°F)

Fever is defined as temperature $\geq 38.0^{\circ}\text{C} / 100.4^{\circ}\text{F}$ (regardless of the location of measurement). The preferred location for measuring temperature in this study will be the oral cavity. Body temperature will also be summarized by 0.5°C increments as follows: $\geq 38.0, > 38.5, > 39.0, > 39.5, > 40.0^{\circ}\text{C}$.

Each subject's data will be summarized according to the maximal severity observed during the follow-up period for each adverse event and each dose, followed by a summary across subjects and across doses.

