10.1.2.3. Daily recording of solicited symptoms

10.1.2.3.1. Studies with electronic diaries

For studies using electronic diaries for the collection of solicited symptoms, symptoms will be considered present only when a daily recording of grade 1 or more is present.

CONFIDENTIAL208851 (RSV OA=ADJ-002)
Statistical Analysis Plan Amendment 2**10.1.2.4. Unsolicited adverse events**

Missing severity, relationship with study vaccine, and outcome of unsolicited adverse events will not be replaced and will appear as 'UNKNOWN' in all statistical output.

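### Section 9.2 fills diary gaps, even inside Days 1-7, only for solicited events ongoing at Day 7, so the same gap gives different symptom durations, against the no-replacement rule in 5.4.2.1

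*SAP*

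**What the plan says.** **Collection and the general rule.** SAP section 5.4.2.1: "Solicited adverse events will be reported daily during the 7-day (from Day 1 to Day 7) follow up period after each vaccination, using structured diaries". It continues: "Missing or non-evaluable measurements will not be replaced". For electronic diaries, section 10.1.2.3.1 adds that "symptoms will be considered present only when a daily recording of grade 1 or more is present". Section 10.1.3.6 defines the duration of a solicited event as the sum of the days reported at grade 1 or higher, and refers to section 9.2 for ongoing symptoms.

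**Planned tables.** Section 5.4.2 asks for the number of days with each solicited symptom in the 7-day period. It wants this repeated for Grade 3 and for all the time after vaccination; the aim of the longer period is "to include the total number of days for symptoms ongoing beyond the follow-up period". Template Table 37 serves both periods. It shows mean, minimum, quartiles and maximum over doses with the symptom.

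**The special rule.** Section 9.2 opens: "When a solicited AE is ongoing at the end of the solicited follow up period (Day 7), the following rules will be applied". Three rules follow:
- If information exists for each day to the end of the event, count up to the last day reported.
- If days are missing between the first day of the event and its end, "count missing days as days with an event (worst case scenario".
- For Grade 3, "take into account the grading of the last day with AE reported (last observation carried forward".

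**The concern.** Whether a gap is filled depends on the outcome being measured. A symptom still present at Day 7 has its earlier missing days counted; a symptom over by then does not. The window for filling starts at the first day of the event, so it covers Days 1-7, where 5.4.2.1 says nothing is replaced.

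Section 9.2 also does not say whether it feeds the 7-day table, the whole-period table or both. One programmer following 5.4.2.1 and 10.1.2.3.1, and another following 9.2, would produce different 7-day tables, and each could cite the SAP.

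What is at stake is the comparison of symptom days and Grade 3 days between formulations and between pools by adjuvant content. If persistence at Day 7 differs between groups, so does the amount of filling, and Template Table 37 has no row that separates recorded from filled days.

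**Working it through.** The SAP states no figure on this point, so there is nothing to reproduce. The diaries below are hypothetical and serve only to apply the rules as worded.

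**Inputs.** Filling runs from the first event day to the end of the event, for events ongoing at Day 7 only (9.2). Otherwise duration is the sum of recorded days (10.1.3.6).

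**Step 1: the same gap, two Day 7 states.** In both diaries Days 1, 2 and 6 are recorded at grade 1 and Days 3-5 are missing.
- Present and ongoing at Day 7: recorded days = 4; under 9.2, Days 1 to 7 = 7.
- Recorded absent on Day 7: recorded days = 3; 9.2 does not apply, so the count is 3. Filled the same way it would be Days 1 to 6 = 6.

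The recorded difference is 4 - 3 = 1 day. The tabulated difference is 7 - 3 = 4 days, and 3 of those 4 come from the rule.

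**Step 2: a longer gap and an end after Day 7.** Days 1-2 are recorded at grade 1, Days 3-6 are missing, the symptom is present on Day 7, the event ends on Day 14, and nothing is recorded after Day 7. Recorded days = 3. Under 9.2, Days 1-7 give 7 and the whole period gives 14.

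**Step 3: Grade 3 days.** Take the Step 2 diary with Grade 3 recorded on Day 7 only, so recorded Grade 3 days = 1. Carry-forward gives end day - 7 + 1:

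| Event ends on Day | Grade 3 days recorded | Grade 3 days under 9.2 |
|---|---|---|
| 8 | 1 | 2 |
| 10 | 1 | 4 |
| 14 | 1 | 8 |
| 30 | 1 | 24 |

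If the Day 7 grade is 1, both counts are 0 for every end day.

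**Step 4: effect on a group mean.** Suppose a share p of the doses with the symptom are ongoing at Day 7, and those doses have on average m missing days between the first event day and Day 7. Applying 9.2 raises the 7-day mean by p × m. With Day 1 and Day 7 both recorded, m cannot exceed 7 - 2 = 5. For equal m, two groups differ by an extra (p1 - p2) × m, which is zero when persistence is equal. The SAP gives neither p nor m.

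**Step 5: the Step 2 diary under the proposed rule.** The 7-day table shows 3. The whole-period table shows 3 recorded days, and 3 + 7 = 10 as worst case (Days 8-14 filled). With Grade 3 on Day 7, it shows 1 recorded Grade 3 day and 1 + 7 = 8 as worst case.

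**The case against.** The best defence is that 9.2 is a deliberate special rule. Section 9 supplements the standard rules in 10.1, and 10.1.3.6 points to 9.2 for ongoing symptoms. The whole-period table exists for events that outlast the window. The rule is openly labelled a worst case, and the days it fills lie between the start and end of an event. Some of them will be true symptom days, so recorded-only counts would understate duration. This much stands: a conservative upper bound is defensible for a descriptive safety duration. It does not settle why gaps inside Days 1-7 are treated differently by Day 7 status, why 5.4.2.1 and 10.1.2.3.1 name no exception, or which table is meant.

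A reader might infer three stronger claims that the document does not support:
- *Graded recording stops at Day 7, so every later Grade 3 day is imputed.* Section 5.4.2.1 defines daily reporting for Days 1-7 but does not say that recording ends there for ongoing events. The first rule of 9.2 allows for daily information to the end of the event, and where that exists nothing is filled. Collection after Day 7 may be set out in the protocol, which is not at hand.
- *The rule invents symptom days, always upward.* The filled days are bracketed by the event, and carrying forward grade 1 or 2 adds no Grade 3 days.
- *Differences between formulations are inflated.* No frequency of gaps, of ongoing events or of imbalance between groups is given. Formulations with more reactions at Day 7 may also truly have longer ones. Distortion is possible but not shown.

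**Conclusion.** The point holds as a minor inconsistency with a cheap remedy. Three things are established from the text: gap filling depends on Day 7 status and, as worded, reaches inside Days 1-7; it contradicts the unqualified rule in 5.4.2.1 and the recorded-grade rule in 10.1.2.3.1; and the table it governs is not named.

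For one diary, the rule can add up to 5 days inside the window when Days 1 and 7 are recorded. For Grade 3, it can turn 1 recorded day into 8 for an event ending on Day 14 with no later record. Both figures rest on constructed diaries; how often such gaps occur is unknown. Only the number-of-days tables are affected. Incidence and maximum grade do not use 9.2, and the SAP treats the safety analyses as descriptive.

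**What to change.** - In the 7-day table, count recorded days only, for every event, whether or not it is ongoing at Day 7.
- Limit the gap filling and the grade carry-forward in 9.2 to days after Day 7, and state that they apply to the whole-period table only.
- In that table, show recorded days beside the labelled worst-case count, for any grade and for Grade 3. The carried-forward Grade 3 count can stay, provided it is labelled; dropping it would trade a conservative count for a possible undercount.
- Name 9.2 as the exception in 5.4.2.1 and 10.1.2.3.1.

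Cost: a few lines of SAP text, a small change to the derivation, and one extra row per symptom in the whole-period version of Template Table 37. The downside is that true symptom days falling in diary gaps within Days 1-7 are not counted.

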10. ANNEXES

10.1. Business rules for standard data derivations and statistical methods

This section contains GSK Vaccines' standard rules for data display and derivation for clinical and epidemiological studies. These rules will be applied along with those detailed in section 9 (additional study-specific rules).

10.1.1. Attributing events to vaccine doses

The dose relative to an event is the most recent study dose given to a subject prior to the start of a given event. For example, if the start date of an adverse event is between Dose 1 and Dose 2, the relative dose will be Dose 1.

If an event starts on the same day as a study dose, the relative dose will be derived from the additional information provided in the CRF using the contents of the flag indicating if the event occurred before or after vaccination. If 'after vaccination' is selected, the relative dose for the event will be the one administered on the start day of the event. If 'before vaccination' is selected, the relative dose for the event will be the dose prior to this one.

10.1.2. Handling of missing data

10.1.2.1. Dates

When partially completed dates (i.e. with missing day or month) are used in calculations, the following standard rules will be applied:

- A missing day will be replaced by 15
- A missing day and month will be replaced by June 30th.

See also exceptions in section 9.1.

10.1.2.2. Laboratory data

Missing laboratory results (including immunological data) will not be replaced.

10.1.2.3. Daily recording of solicited symptoms

10.1.2.3.1. Studies with electronic diaries

For studies using electronic diaries for the collection of solicited symptoms, symptoms will be considered present only when a daily recording of grade 1 or more is present.

CONFIDENTIAL208851 (RSV OA=ADJ-002)
Statistical Analysis Plan Amendment 2**10.1.2.4. Unsolicited adverse events**

Missing severity, relationship with study vaccine, and outcome of unsolicited adverse events will not be replaced and will appear as 'UNKNOWN' in all statistical output.

10.1.3. Data derivation**10.1.3.1. Age at vaccination in years**

When age at vaccination is to be displayed in years, it will be calculated as the number of complete calendar years between the date of birth and the date of vaccination. For example:

DOB = 10SEP1983, Date of vaccination = 09SEP2018 -> Age = 34 years

DOB = 10SEP1983, Date of vaccination = 10SEP2018 -> Age = 35 years

10.1.3.2. Temperature

Temperatures will be presented in degrees Celsius (°C). Temperatures reported in degrees Fahrenheit (°F) will be converted as follows:

Temperature (Celsius) = ((Temperature (Fahrenheit) - 32) x 5)/9

Conversion of temperature from °Fahrenheit to °C will be performed according to SDTM specifications.

10.1.3.3. Numerical serology results

Numerical serology results will be derived from the content of IS.ISORRES in the SDTM dataset. For assays with a specific cut-off, the following derivation rules apply:

IS.ISORRES	Derived value
"NEG", "-", or "(-)"	cut-off/2
"POS", "+", or "(+)"	cut-off
"< value" and value is <= assay cut-off	cut-off/2
"< value" and value is > assay cut-off	value
"> value" and value is < assay cut-off	cut-off/2
"> value" and value is >= assay cut-off	value
"value" and value is < cut-off	cut-off/2
"value" and value is >= cut-off and value is <= ULOQ	value
"value" and value is > ULOQ	ULOQ*
All other cases	missing

*This rule will be used to compute descriptive statistics (GMTs, fold increase, etc). All values might be displayed in RCCs and scatter plots with individual results.

CONFIDENTIAL208851 (RSV OA=ADJ-002)
Statistical Analysis Plan Amendment 2**10.1.3.4. Geometric mean titers (GMTs) and concentrations (GMCs)**

Geometric Mean Titer (GMT) or Concentration (GMC) calculations are performed by taking the inverse logarithm of the mean of the log titer or concentration transformations. Antibody titers or concentrations below the cut-off of the assay will be given an arbitrary value of half the cut-off of the assay for the purpose of GMT/GMC calculation. The cut-off value is defined by the laboratory before the analysis and is described in the protocol.

10.1.3.5. Onset day

The onset day for an event (e.g. AE, medication, vaccination) is the number of days between the last study vaccination and the start date of the event. This is 1 for an event occurring on the same day as a vaccination (and reported as starting after vaccination).

10.1.3.6. Duration of events

The duration of an event with a start and end date will be the number of days between the start and end dates plus one day, i.e. an event that starts on 03MAR2018 and ends on 12MAR2018 has a duration of 10 days.

The duration of solicited events will be calculated as the sum of the individual days with the symptom reported at grade 1 or higher.

See also specific rules for ongoing symptoms in section [9.2](#).

10.1.3.7. Counting rules for combining solicited and unsolicited adverse events

For output combining solicited and unsolicited adverse events, all serious adverse events will be considered general events since the administration site flag is not included in the expedited adverse event CRF pages.

Multiple events with the same preferred term which start on the same day are counted as only one occurrence.

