The test and the 95% CIs for treatment comparisons will be calculated according to the delta method on the log-transformed ratio of RSVPref3-specific frequency relative to the background frequency estimates.

For each comparison, the covariance matrix of the means is pre multiplied and post-multiplied by the vector of partial derivative to provide the variance of the contrast:

$$\text{Var}\left(\text{Log}_{10}\left(\frac{\hat{Z}_{jk_2}}{\hat{Z}_{jk_1}}\right)\right) = T\left(\nabla_{\hat{Y}_{jk_1}, \hat{Y}_{jk_2}}(\bullet)\right) \cdot \sum \cdot \nabla_{\hat{Y}_{jk_1}, \hat{Y}_{jk_2}}(\bullet)$$

Where

\sum is the covariance matrix, and

$$\nabla_{\hat{Y}_{jk_1}, \hat{Y}_{jk_2}}(\bullet) = \nabla_{\hat{Y}_{jk_1}, \hat{Y}_{jk_2}}\left(\text{Log}_{10}\left(\frac{\hat{Z}_{jk_2}}{\hat{Z}_{jk_1}}\right)\right) = \begin{pmatrix} -1 - \frac{1}{\hat{Z}_{jk_1}} \\ 1 + \frac{1}{\hat{Z}_{jk_2}} \end{pmatrix}$$

The $\text{Log}_{10}(W_{jk})$ confidence interval is calculated based on the T-student percentile using the degrees of freedom provided by the MIXED procedure for the difference of means under consideration (eg Y_{jk_2} and Y_{jk_1}) and the standard error calculated above.

$$\text{Log}_{10}\left(\text{LowerCI}(W_{jk})\right) = \text{Log}_{10}\left(\frac{\hat{Z}_{jk_2}}{\hat{Z}_{jk_1}}\right) - \text{TINV}(1 - \text{alpha}/2, df) \cdot \sqrt{\text{Var}\left(\text{Log}_{10}\left(\frac{\hat{Z}_{jk_2}}{\hat{Z}_{jk_1}}\right)\right)}$$

The confidence intervals are then back-transformed to the original units to provide the confidence intervals for W_{jk} . (Amendment 2 – 17 MAR 2020).

CONFIDENTIAL208851 (RSV OA=ADJ-002)
Statistical Analysis Plan Amendment 2**5.4. Analysis of safety and reactogenicity****5.4.1. Analysis of safety and reactogenicity planned in the protocol**

The percentage of subjects with at least one local AE (solicited and unsolicited), with at least one general AE (solicited and unsolicited) and with any AE during the 7-day or 30-day follow-up period will be tabulated with exact 95% confidence interval (CI) after each dose and overall. The same computations will be done for Grade 3 AEs, for any AEs considered related to vaccination, for Grade 3 AEs considered related to vaccination and for Grade 3 non-serious AEs.

The percentage of subjects with any AE (solicited and unsolicited) resulting in a medically attended visit during the 30-day follow-up period will also be tabulated after each dose and overall.

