The percentage of subjects reporting each individual solicited local AE (any grade and Grade 3) and solicited general AE (any grade, Grade 3, any related and Grade 3 related) during the 7-day follow-up period (i.e., on the day of vaccination and 6 subsequent days) will be tabulated for each group after each dose and overall.

For fever, the number and percentage of subjects reporting fever by half degree (°C) cumulative increments during the 7-day follow-up period (i.e., on the day of vaccination and 6 subsequent days) will be tabulated for each group after each dose and overall. Similar tabulations will be performed for any fever with a causal relationship to vaccination and for Grade 3 ($> 39.0^{\circ}\text{C}/102.2^{\circ}\text{F}$) causally related fever.

For each group and for each hematology and biochemistry parameter:

- The percentage of subjects having hematology and biochemistry results below or above the laboratory normal ranges will be tabulated by time point.
- The summary of grading post-vaccination will be tabulated versus baseline. (Grades will be based on the FDA Guidance for Industry “Toxicity Grading Scale for Healthy Adults and Adolescent Volunteers Enrolled in Preventive Vaccine Clinical Trials”, see APPENDIX C in the protocol. Those laboratory parameters not included on FDA Toxicity Grading Scale will not be graded).

The percentage of subjects with any unsolicited AEs during the 30-day follow-up period (i.e., on the day of vaccination and 29 subsequent days) with its exact 95% CI will be tabulated by group and by Medical Dictionary for Regulatory Activities (MedDRA) preferred term. Similar tabulation will be done for Grade 3 unsolicited AEs, for any causally related unsolicited AEs, for Grade 3 causally related unsolicited AEs and for unsolicited AEs resulting in a medically attended visit. The verbatim reports of unsolicited AEs will be reviewed by a physician and the signs and symptoms will be coded according to the MedDRA Dictionary for Adverse Reaction Terminology. Every verbatim term will be matched with the appropriate Preferred Term.

The percentage of subjects with at least one report of SAE classified by the MedDRA Preferred Terms and reported during the entire study period will be tabulated with exact 95% CI. SAEs will also be described in detail.

CONFIDENTIAL

208851 (RSV OA=ADJ-002)
Statistical Analysis Plan Amendment 2

For Part A only, pregnancy and pregnancy outcomes will be listed (if applicable).

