12.4. Safety

Template Table 32 Compliance in completing solicited adverse events information (Exposed Set)

DOSE	<Each group>		
	N	n	Compliance (%)
Vaccination at Visit 1	xxx	xxx	xx.X
Vaccination at Visit 4	xxx	xxx	xx.X
TOTAL	xxx	xxx	xx.X

Short group label = long group label

N=Number of administered vaccinations

n = number of vaccinations with solicited symptom information completed

Compliance (%) = (n / N) X 100

CONFIDENTIAL

208851 (RSV OA=ADJ-002)
 Statistical Analysis Plan Amendment 2

Template Table 33 Incidence and nature of <grade 3> symptoms (solicited and unsolicited) <with causal relationship to vaccination> reported during the XX-day (Days 1-XX) post-vaccination period following each dose and overall <analysis set name>

		<Each group>					<Each group>				
					95% CI					95% CI	
Dose	Symptoms	N	n	%	LL	UL	N	n	%	LL	UL
DOSE 1	Any symptom	xxx	xxx	xx.x	xx.x	xx.x	xxx	xxx	xx.x	xx.x	xx.x
	General symptoms	xxx	xxx	xx.x	xx.x	xx.x	xxx	xxx	xx.x	xx.x	xx.x
	Local symptoms	xxx	xxx	xx.x	xx.x	xx.x	xxx	xxx	xx.x	xx.x	xx.x
DOSE 2	Any symptom	xxx	xxx	xx.x	xx.x	xx.x	xxx	xxx	xx.x	xx.x	xx.x
	General symptoms	xxx	xxx	xx.x	xx.x	xx.x	xxx	xxx	xx.x	xx.x	xx.x
	Local symptoms	xxx	xxx	xx.x	xx.x	xx.x	xxx	xxx	xx.x	xx.x	xx.x
OVERALL/DOSE	Any symptom	xxx	xxx	xx.x	xx.x	xx.x	xxx	xxx	xx.x	xx.x	xx.x
	General symptoms	xxx	xxx	xx.x	xx.x	xx.x	xxx	xxx	xx.x	xx.x	xx.x
	Local symptoms	xxx	xxx	xx.x	xx.x	xx.x	xxx	xxx	xx.x	xx.x	xx.x
OVERALL/SUBJECT	Any symptom	xxx	xxx	xx.x	xx.x	xx.x	xxx	xxx	xx.x	xx.x	xx.x
	General symptoms	xxx	xxx	xx.x	xx.x	xx.x	xxx	xxx	xx.x	xx.x	xx.x
	Local symptoms	xxx	xxx	xx.x	xx.x	xx.x	xxx	xxx	xx.x	xx.x	xx.x

Short group label = long group label

For each dose:

N = number of subjects with the corresponding administered dose

n/% = number/percentage of subjects presenting at least one type of symptom following the corresponding dose

For overall/dose:

N = number of administered dose

n/% = number/percentage of doses followed by at least one type of symptom

For overall/subject:

N = number of subjects with at least one administered dose

n/% = number/percentage of subjects presenting at least one type of symptom

95% CI = Exact 95% confidence interval; LL = lower limit, UL = upper limit

CONFIDENTIAL208851 (RSV OA=ADJ-002)

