Template Table 40 Listing of potential immune-mediated disorders (pIMDs) reported as identified by predefined list of preferred terms and/or by investigator assessment <analysis set name>

Group	Sub. Group	Gender	Country	Race	Age at onset (Year)	Verbatim	Preferred Term	Primary System Organ Class
<each group>								

Group	Sub. Group	Medical visit type	Dose	Day of onset	Duration	Intensity	Causality	Outcome	SAE (Y/N)	pIMD source
<each group>										

Short group label = long group label

CONFIDENTIAL208851 (RSV OA=ADJ-002)
Statistical Analysis Plan Amendment 2**Template Table 41 Listing of SAEs <analysis set name>**

Group	Sub. No.	Gender	Country	Race	Age at onset (Year)	Verbatim	Preferred Term
<each group>							

Group	Sub. No.	Primary System Organ Class	Medical visit type	Dose	Day of onset	Duration	Intensity	Causality	Outcome
<each group>									

Short group label = long group label

Template Table 42 Listing of pregnancies reported during the study period in Part A <analysis set name>

Group	Sub. No.	Count	Race	Age at vaccination	Previous Dose	LM P date	Days between LMP-vacc	Age at delivery (Year)	Date of delivery	Pregnancy Outcome	Date of outcome	Gestational weeks at birth/miscarriage/termination

Short group label = long group label

LMP=Last Menstrual Period

CONFIDENTIAL208851 (RSV OA=ADJ-002)
Statistical Analysis Plan Amendment 2**Template Table 43 Number and percentage of subjects taking concomitant medication during the <XX>-day (Days 1-<XX>) post-vaccination period by dose and overall <analysis set name>**

Dose		<Each group>					<Each group>				
		<95>% CI			<95>% CI		<95>% CI			<95>% CI	
		N	n	%	LL	UL	N	N	%	LL	UL
DOSE x	Any	xx	xx	xx.x	xx.x	xx.x	xx	Xx	xx.x	xx.x	xx.x
	Antipyretics										
	Prophylactic antipyretics	xx	xx	xx.x	xx.x	xx.x	xx	Xx	xx.x	xx.x	xx.x
OVERALL/DOSE	Any	xx	xx	xx.x	xx.x	xx.x	xx	Xx	xx.x	xx.x	xx.x
	Antipyretics										
	Prophylactic antipyretics	xx	xx	xx.x	xx.x	xx.x	xx	Xx	xx.x	xx.x	xx.x
OVERALL/SUBJECT	Any	xx	xx	xx.x	xx.x	xx.x	xx	Xx	xx.x	xx.x	xx.x
	Antipyretics										
	Prophylactic antipyretics	xx	xx	xx.x	xx.x	xx.x	xx	Xx	xx.x	xx.x	xx.x

Short group label = long group label

For each dose:

N = total number of subjects with the corresponding administered dose

n/% = number/percentage of subjects who took the specified type of concomitant medication at least once during the considered period

For overall/dose:

N = number of administered doses

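### In tables that combine solicited and unsolicited AEs, a serious injection-site reaction counts as general and can be missing from the local row

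*SAP*

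**What the plan says.** The rule is in the standard business rules of the SAP, section 10.1.3.7. It is limited to outputs that combine solicited and unsolicited AEs, where "all serious adverse events will be considered general events since the administration site flag is not included in the expedited adverse event CRF pages".

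Section 5.4.1 plans outputs of that kind: the percentage of subjects with at least one local AE, at least one general AE and any AE, solicited and unsolicited together, over 7 or 30 days after each dose and overall, with exact 95% confidence intervals. It then extends them: "The same computations will be done for Grade 3 AEs, for any AEs considered related to vaccination, for Grade 3 AEs considered related to vaccination". A further version covers Grade 3 non-serious AEs. The display shell is "Template Table 33 Incidence and nature of <grade 3> symptoms (solicited and unsolicited) <with causal relationship to vaccination> reported during the XX-day" and so on, with rows for Any, General and Local symptoms. Its title does not exclude SAEs and its footnotes do not mention the counting rule.

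Two other sets of outputs matter for scope. Section 5.4.2 tabulates solicited events alone: "The percentage of subjects with at least one local solicited AE, with at least one general solicited AE and with any solicited AE". SAEs also have their own table: "The percentage of subjects with at least one report of SAE classified by the MedDRA Preferred Terms and reported during the entire study period" is tabulated with an exact 95% CI. Template Table 41, "Listing of SAEs", shows verbatim term, Preferred Term, intensity and causality for each event.

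**The concern.** The rule is driven by a gap in a CRF page and not by where the reaction occurred. A serious reaction at the injection site is a local event by any ordinary reading, yet the combined table files it under general. The shift goes one way: the rule can take events out of the local row and never puts any in, and the events it takes out are serious ones. A reader of Template Table 33 would not know this, because nothing on the table says so. The information needed to place such an event is largely collected already, since every SAE has a verbatim term and a coded Preferred Term.

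At stake is the accuracy of the local and general rows of one family of tables, in a trial that aims to describe differences in reactogenicity between groups (SAP section 6).

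**Working it through.** The SAP gives no rate or count for this point, so there is no stated figure to reproduce. The check has three parts.

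**1. Which outputs the rule reaches**

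| Output | Combines solicited and unsolicited, with a local/general split? | Affected? |
|---|---|---|
| 5.4.1 and Template Table 33, Local and General rows (any, Grade 3, related, Grade 3 related) | Yes, SAEs not excluded | Yes |
| Same table, Any symptom row | No split | No |
| Grade 3 non-serious version | SAEs excluded by definition | No |
| Solicited local tables (5.4.2, Template Table 35) | Solicited only | No |
| Template Table 47 | SAEs excluded | No |
| SAE table and listing (Template Tables 48 and 41) | By Preferred Term | No |

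No section moves an injection-site SAE back to local in the affected rows.

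**2. What has to happen for a row to change**

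The rates count subjects with at least one event. The Local row loses a subject only if (a) an injection-site SAE starts inside the 7- or 30-day window, (b) the subject has no other local event that qualifies for that row, and (c) for the Grade 3 or related rows, the SAE is itself Grade 3 or related. The General row gains the subject only if there is no other qualifying general event.

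Condition (b) is not trivial. Pain, redness and swelling are recorded daily for 7 days (sections 5.4.2.1 and 5.4.2.3), and nothing says that a diary entry is removed when the reaction is also reported as an SAE. The exposed cases are mainly reactions that start after Day 7 or that are not one of those three symptoms.

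**3. Size per affected subject**

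Inputs: about 70 + 30 = 100 subjects per Part B group and about 12 per Part A group (section 2); Clopper-Pearson intervals (section 10.1.5.1).

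Shift in a row = 1/N: 1/100 = 1.0 percentage point in Part B, 1/12 = 8.3 percentage points in Part A.

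For zero cases, the upper limit is 1 − 0.025^(1/N). For one case, the lower limit is 1 − 0.975^(1/N) and the upper limit is the 97.5% quantile of Beta(2, N − 1). Illustration, assuming one subject per group whose only qualifying local event is serious:

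| Group | Local row under the rule | Local row with the event classed by site |
|---|---|---|
| Part B, N = 100 | 0/100 = 0% (0 to 3.6%) | 1/100 = 1.0% (0.03 to 5.4%) |
| Part A, N = 12 | 0/12 = 0% (0 to 26.5%) | 1/12 = 8.3% (0.2 to 38.5%) |

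Under section 10.1.4.1 an exact zero prints as 0%, so in this case the row would read as if no such reaction had occurred.

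The number of injection-site SAEs is not in the document. As an assumption only, 0 to 0.1% per dose over 9 RSV groups × 100 subjects × 2 doses = 1,800 Part B doses gives 0 to 1.8 events. That is before condition (b) removes any of them.

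**The case against.** The best defence is that this is a fixed, disclosed convention with a stated reason, applied identically to every group, and that it hides nothing. Any such event appears by Preferred Term in the SAE table and, with verbatim, intensity and causality, in the SAE listing. With so few expected cases, that is where a reader would look for them. The alternative needs judgement, because coded terms do not always name the site: section 5.4.2.3 itself maps solicited redness to the site-free term Erythema.

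Much of this stands. It keeps the point small, and it means the remedy cannot rest on Preferred Terms alone. It does not make the Local and General rows correct, and the disclosure sits in an annex and not on the table.

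Three stronger readings are tempting and are not supported:

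- A reader might infer that serious local reactions drop out of the local and Grade 3 local rates generally. The opening words of the rule limit it to combined outputs, and solicited-only tables are outside it.
- A reader might infer that the primary endpoints are biased. Section 3.2.1 lists solicited events, unsolicited events, laboratory abnormalities, Grade 3 non-serious events, SAEs and, in Part B, pIMDs. None is a combined local rate that includes SAEs, and SAEs count in their own right whatever their site.
- A reader might infer that the comparison of AS01B, AS01E and Plain on local tolerability is distorted. The pooling by adjuvant content in section 5.4.2 is specified for solicited symptoms, which the rule does not touch.

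**Conclusion.** The point holds for the Local and General rows of the combined tables and no further. Followed as written, the rule classes a serious injection-site reaction as general, and the Local row omits the subject unless another qualifying local event keeps them in. The error runs in one direction for each row: Local can only be too low and General only too high. Its size is at most 1/N per affected subject, which is 1 percentage point in a Part B group of about 100 and 8.3 points in a Part A group of about 12. How many subjects would be affected is unknown. The 0 to 1.8 events above rest on an assumed rate and include zero. This is a minor improvement to make, and it does not threaten the safety conclusions.

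**What to change.** Amend section 10.1.3.7 so that, in outputs combining solicited and unsolicited AEs, an SAE is classified as local when its MedDRA term or verbatim identifies an injection-site event, and as general otherwise. Make the classification by blinded review of SAE terms before the first analysis, which is when the statistician is unblinded (section 7.1). The windows of the combined tables close 30 days after Dose 2, so one review on the data for that analysis covers every affected event. Apply the result to all versions of Template Table 33 that include SAEs. Footnote the table with the rule, and list any SAE whose site cannot be determined.

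The cost is a change of SAP wording and a short blinded term review. No new data are needed. The downside is some judgement where the coded term does not name the site, as with Erythema; the list of undetermined cases keeps that judgement visible.
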